This project will utilize sensitive, early biomarkers of disease risk, including whole-body adiposity, hepatic triglyceride content and carotid IMT, directly relevant to diabetes and cardiovascular disease risk, respectively. **The overall aim of this two-study research plan is to characterize risk using these sensitive biomarkers in children with mental health disorders, and evaluate the magnitude of change observed in these biomarkers in children receiving an established weekly behavioral weight-loss (BWL) intervention.** This will be accomplished with a randomized, controlled test of the effects of a 16-week behavioral weight loss intervention on CTGC, PDFF and IMT in overweight/obese antipsychotic (AP)-treated children randomized 2:1 to weekly BWL treatment or monthly diet and exercise education or usual care (UC), versus nonpsychiatric (NP) overweight or obese children undergoing the weekly BWL treatment.

Study Aims for this pilot randomized controlled trial:

Aim 1: To evaluate the main effect of time of 16 weeks of a BWL intervention on DEXA-measured whole body adiposity in overweight/obese antipsychotic (AP)-treated children compared to nonpsychiatric (NP) overweight or obese healthy controls, and in AP-treated youth randomized to monthly Usual Care (UC).

Aim 2: To evaluate the main effect of time of 16 weeks of a BWL intervention on PDFF in overweight/obese AP-treated children compared to NP overweight or obese healthy controls, and in AP-treated youth randomized monthly UC.

Aim 3: To evaluate the main effect of time of 16 weeks of a weekly behavioral weight loss intervention on CIMT in overweight/obese AP-treated children compared to NP overweight or obese healthy controls, and in AP-treated youth randomized monthly UC.

Primary Hypothesis: *Change in DEXA-measured total fat and PDFF/IMT will be more pronounced in the weekly weight loss intervention groups compared to the monthly Usual Care intervention.*

Exploratory Aims:

a) To evaluate the effects of 16 weeks' of weekly versus monthly weight loss intervention on changes in standard cardiometabolic risk factors (e.g., fasting lipids, insulin, glucose, adiponectin, fibrinogen, high sensitivity C-reactive protein and very low density lipoprotein particle size).

b) To evaluate baseline psychiatric symptom severity on treatment adherence and changes in biomarkers during treatment.

PARTICIPANT RECRUITMENT & SELECTION

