Inclusion Criteria: **i)** 6-18 years old (at any point during study participation); **ii)** BMI percentile \geq 85 **iii)** Meet DSM-IV criteria for one or more childhood onset psychiatric disorders including disruptive behavior disorders (attention deficit disorder, conduct disorder, oppositional defiant disorder and disruptive behavior disorder not otherwise specified), affective disorders (bipolar affective disorder, major depressive disorder and mood disorder not otherwise specified), anxiety disorders (generalized anxiety disorder, obsessive compulsive disorder, separation anxiety, social and other specific phobias) as well as other disorders, including autism spectrum disorders (autistic disorder, Asperger's Syndrome and pervasive developmental disorder not otherwise specified), psychotic disorders (schizophreniform disorder, schizophrenia and psychotic disorder not otherwise specified) and movement disorders (tic disorder, Tourette's Syndrome) (*EXCEPT* for the Obese or Overweight Control Group, none of whom can meet criteria for any DSM-IV Axis I psychiatric illness); **iv)** Participants treated with psychotropic medication may not have any medication changes for 1 month prior to study enrollment at the discretion of the PI, and Antipsychotic-Treated Participants must be treated with an antipsychotic \geq approximately 6 months with no antipsychotic medication dose changes for 1 month; **vi)** The Healthy Overweight or Obese Control Group may not be currently taking any prescription medications (multivitamins, over the counter medications, glucocorticoid nasal spray and inhalers are permitted, as well as non-sedating antihistamines such as but not limited to Claritin (loratadine) and Zyrtec (cetirizine)); and **vii)** Participants between 6-17 years old able to give assent and have a parent/guardian that can provide written informed consent, and 18 year-old participants will be able to provide written informed consent.

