Analytic approach: the primary goal was to compare changes over time in the three risk factors (CIMT/DEXA/PDDF) among three groups: obese AP-treated children randomized to the weekly intervention, obese NP children also receiving weekly behavioral weight loss treatment, and an obese usual care (UC) reference group. Comparisons of interest were between each of the two active treatment groups and UC, as well as between the two active intervention groups themselves (AP-treated vs. NP). Because this is a pre-post design with data collected only at baseline and at 16 weeks, our analytic strategy used an analysis of covariance (ANCOVA), in which the 16-week value of the risk factor is the dependent variable and the predictors are the baseline value of the risk factor and the study group (three level factor), with contrasts of interest listed above. Other analyses performed adjusted for covariates such gender and age to determine whether baseline-adjusted between group differences at 16 weeks can be explained by such covariates. Because of the relatively small sample size in this study, we performed separate analyses of covariance that include precisely one additional covariate, in addition to the baseline value of the risk factor of interest in each analysis.

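### ANCOVAs that add one covariate at a time cannot show that age and sex together fail to explain the non-randomized differences (AP weekly vs NP, NP vs UC)

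*Combined protocol and SAP*

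**What the plan says.** The Analytic approach (Appendix I, Data Management, Safety & Adverse Event Reporting) sets out a main ANCOVA of the 16-week value on its baseline value and a three-level group factor. The contrasts are each active group against usual care (UC), and AP weekly against NP.

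It then describes further models: "Other analyses performed adjusted for covariates such gender and age". Their purpose is "to determine whether baseline-adjusted between group differences at 16 weeks can be explained by such covariates". The form is restricted: "Because of the relatively small sample size in this study", "we performed separate analyses of covariance that include precisely one additional covariate". No model holding age and sex together is described.

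Under Specific Aims, only the AP-treated children are randomized (2:1). They are studied "versus nonpsychiatric (NP) overweight or obese children undergoing the weekly BWL treatment", so NP is a separately recruited group. Participant Recruitment & Selection gives NP its own referral sources, allows ages 6 to 18 and describes no matching.

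**The concern.** The covariate models are there to settle whether a difference is explained by covariates. For AP weekly vs NP and NP vs UC, age and sex can differ between groups at the same time. A model with age alone leaves the sex part of the confounding, and a model with sex alone leaves the age part. A difference produced by the two together can therefore survive both models and be reported as not explained by either. If the two act in opposite directions, adjusting for one can move the estimate further from the truth than no adjustment.

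What is at stake is the interpretation of the two non-randomized contrasts. The reason given for the restriction also needs checking, because a joint model with two one-parameter covariates is not obviously too large for this trial.

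**Working it through.** **1. The plan's own power figures.** Noncentral F for three groups, N = 60, λ = f²N, df = (2, 57). For f = 0.49, λ = 0.2401 × 60 = 14.4. Results for f = 0.16, 0.49 and 0.53 are 0.174, 0.922 and 0.956, against 0.17, 0.92 and 0.96 in the Power section. They reproduce.

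**2. Number analysed.** Most group comparisons in Appendix II Table 2 have F[2,34]. The base ANCOVA has 4 parameters (intercept, baseline, two for group), so N = 34 + 4 = 38. The printed means of whole-number measures fit 15 AP weekly and 17 NP, leaving 38 − 15 − 17 = 6 UC. Table 1 prints 17 for AP monthly, but 19 + 17 + 21 = 57 while the combined N is 47. The combined mean weight needs 7: (19 × 77.08 + 7 × 72.37 + 21 × 85.76)/47 = 80.26, as printed.

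**3. Cost in degrees of freedom and power.** Error df = N − 4 − (extra covariates), with age linear.

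| Model | df, N = 60 | df, N = 38 | Critical t, N = 38 |
|---|---|---|---|
| Base ANCOVA | 56 | 34 | 2.032 |
| One extra covariate | 55 | 33 | 2.035 |
| Age and sex together | 54 | 32 | 2.037 |

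At N = 38, power for f = 0.16, 0.49 and 0.53 goes from 0.1229, 0.7356 and 0.8043 (one covariate) to 0.1227, 0.7343 and 0.8031 (joint). The largest loss is 0.13 percentage points.

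**4. Cost in standard error.** For a useless, balanced second covariate the average inflation is about √(1 + 1/32) = 1.016; simulation gives 1.4% (0.220 vs 0.217). If it is useless but imbalanced between groups, the average is about 4% to 5%.

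**5. What each model leaves behind.** All inputs here are assumptions: true AP–NP difference zero; NP 0.5 SD older; 75% male in AP and 50% in NP; effects on the 16-week value given baseline of 0.3 per SD of age and 0.5 for sex, reinforcing each other; baseline slope 0.8; residual SD 0.6; 15/6/17 children. Units are baseline SDs. With age and sex unrelated within groups, the expected bias is:

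- unadjusted: 0.3 × 0.5 + 0.5 × 0.25 = 0.275
- age only: 0.5 × 0.25 = 0.125
- sex only: 0.3 × 0.5 = 0.15
- joint: 0

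Simulation agrees, with false-positive rates of about 18%, 8%, 9% and 5%. The expected bias is the same for NP vs UC if both AP arms share the assumed distribution.

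**6. Other scenarios.**

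- Milder (0.3 SD; 75% vs 50% male; effects 0.2 and 0.3): age only leaves 0.3 × 0.25 = 0.075 and sex only leaves 0.2 × 0.3 = 0.06. Across runs of milder cases like this, the bias was about 0.06 to 0.08 and the false-positive rate about 5% to 7%.
- Only age imbalanced (75% male in both groups): the age-only model has no bias and the nominal error rate, as does the joint model.
- Opposite directions (0.5 SD; effects 0.3 and 0.4): bias 0.05 unadjusted, −0.10 age only, 0.14 sex only, about 0 joint.

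**The case against.** The strongest reply is that joint confounding is not shown. Age and sex by group are not printed, and Table 1 is titled as additional characteristics, so a main table may exist elsewhere. This stands. The only indirect sign is height in Table 2: NP 1.65 m, AP weekly 1.59 m and UC 1.54 m, gaps of about 0.46 and 0.93 pooled SD. Height reflects age and sex without separating them, so it proves nothing.

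A reader might take the 75% vs 50% male split from the 3:1 recruitment target. The documents do not support that. The target appears once, in a paragraph covering both AP and NP, and no 50% figure appears. If 3:1 held in both groups, age adjustment alone would suffice.

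The main scenario is also strong. Much of the dependence of body fat on age and sex is already carried by the baseline term. The assumed covariates alone have SD √(0.09 + 0.25 × 0.1875) = 0.37 in AP. The printed SD of change in DEXA percent fat, over the baseline SD, is 2.63/7.78 = 0.34 (AP weekly), 1.89/7.33 = 0.26 (UC) and 2.63/5.07 = 0.52 (NP). In the milder case the covariate SD is √(0.04 + 0.09 × 0.1875) = 0.24, which fits within all three. So the milder figures deserve at least equal weight.

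It might also be said that the joint model widens intervals by 2% at most. That is an average for a balanced covariate, not a bound. With a useless balanced covariate, 39% of simulated data sets exceeded 2%, and the 95th percentile was 7%.

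Finally, these are additional analyses in a pilot, and the covariate list is open. Both points limit the weight of the finding, but neither makes the stated inference valid.

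**Conclusion.** The point holds in a limited form. When age and sex both differ between groups and both affect the outcome, none of the planned models can answer the question they were set for in the two non-randomized contrasts. Small sample size does not justify the restriction for these two covariates: the joint model has 6 parameters for 38 children.

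The actual size is unknown. Single-covariate bias is about 0.12 to 0.15 SD (false positives 8% to 9%) under strong assumed imbalance in both, about 0.06 to 0.08 SD (5% to 7%) in milder cases, and nil for the right single model if only one covariate is imbalanced.

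A reader might infer that the reported AP–NP differences are confounded, or that the main results are undermined. The documents support neither. No imbalance is shown, the primary ANCOVA is untouched, and AP weekly vs UC is a randomized comparison in which imbalance arises by chance rather than from recruitment.

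**What to change.** Add one adjusted ANCOVA per outcome with baseline, group, age (linear) and sex together. Base any statement that a difference is or is not explained by age and sex on that model, and keep the single-covariate fits as description. The text is partly in the past tense and results are printed, so label the joint model post hoc if it is added after results are known. Reporting age and sex by group beside it would let readers judge whether the question arises.

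No new data are needed. The cost is one error degree of freedom more than each single-covariate model and two more than the base ANCOVA. If the second covariate does not help, the standard error is on average about 1% to 2% larger when it is balanced and about 4% to 5% larger when it is not. If both covariates matter, the joint standard error can be the smallest (0.233 vs 0.239 and 0.250 in the main scenario). Categorized age or further covariates would cost more. Confounding by diagnosis-related differences between AP and NP would remain.

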APPENDIX II: Supplementary Tables and Figures

Table 1: Additional Baseline Clinical Characteristics by Treatment Group. Values presented as mean (SD).

	Combined (N=47)	AP-Treated² (Weekly) (n=19)	AP-Treated² (Monthly) (n=17)	NP¹(Weekly) (n=21)
Study Population Demographics				
Height (m), mean (SD)	1.60 (0.14)	1.58 (0.15)	1.58 (0.17)	1.63 (0.11)
Weight (kg), mean (SD)	80.26 (26.62)	77.08 (32.60)	72.37 (16.11)	85.76 (23.07)
Waist Circumference (cm), mean (SD)	100.83 (16.58)	99.45 (19.35)	99.86 (10.35)	102.40 (16.07)
BMI (kg/m²), mean (SD)	30.52 (5.69)	29.70 (6.83)	28.72 (2.09)	31.86 (5.25)
BMI Percentile, mean (SD)	97.24 (2.60)	96.55 (3.30)	97.77 (1.03)	97.69 (2.16)
BMI Z-Score, mean (SD)	2.06 (0.40)	1.99 (0.47)	2.05 (0.23)	2.13 (0.38)
Percent Overweight, mean (SD)	62.36 (26.50)	57.33 (27.11)	56.91 (14.07)	68.73 (28.60)
Fasting Glucose (mg/dL), mean (SD)	90.02 (7.13)	91.32 (7.42)	93.71 (10.01)	87.62 (4.99)
Fasting Lipids (mg/dL), mean (SD)				
Triglycerides	104.30 (57.35)	106.26 (59.11)	114.43 (44.49)	99.14 (61.30)
Total Cholesterol	164.36 (31.10)	169.47 (37.55)	170.14 (9.67)	157.81 (29.09)
HDL Cholesterol	48.34 (10.04)	46.95 (10.20)	45.00 (6.16)	50.71 (10.74)
LDL Cholesterol	95.32 (24.49)	101.68 (27.32)	102.29 (10.95)	87.24 (23.40)
DEXA Percent Fat, mean (SD)	42.51 (6.97)	41.76 (8.53)	45.40 (6.76)	42.24 (5.38)
DEXA Percent Lean, mean (SD)	54.77 (6.73)	55.48 (8.23)	52.12 (6.81)	55.01 (5.15)
PDDF (%), mean (SD)	6.58 (8.54)	6.52 (8.21)	12.01 (7.82)	4.72 (8.61)
CIMT (cm), mean (SD)	0.0484 (0.0070)	0.0451 (0.0074)	0.0494 (0.0058)	0.0504 (0.0065)
Aberrant Behavior Checklist, mean (SD)				
Total	25.17 (26.11)	35.61 (24.29)	53.43 (20.14)	6.81 (13.39)
Irritability	8.15 (9.13)	11.06 (8.30)	18.57 (8.75)	2.19 (4.81)

Table 2: Change in Additional Metabolic and Behavioral Measures by Treatment Group

Variable (units)	AP-BWI				AP-UC				NP-BWI				Time x Treatment
	Week 0	Week 16	Change	η^2 *	Week 0	Week 16	Change	η^2 *	Week 0	Week 16	Change	η^2 *	
Clinical Outcome Variables													
Height (m)	1.59 (0.15)	1.60 (0.14)	0.02 (0.02)	0.62	1.54 (0.14)	1.56 (0.15)	0.02 (0.02)	0.71	1.65 (0.11)	1.66 (0.11)	0.01 (0.01)	0.40	F[2,34]=1.16, η^2 =0.33
Weight (kg)	78.04 (33.32)	77.93 (32.99)	-0.12 (3.04)	0.00	68.56 (13.77)	70.98 (12.09)	2.42 (2.36)	0.56	88.49 (23.73)	86.19 (24.19)	-2.30 (4.29)	0.23	F[2,34]=3.37, η^2 =0.05
BMI Z-Score	2.01 (0.52)	1.88 (0.63)	-0.13 (0.17)	0.40	2.08 (0.23)	2.05 (0.31)	-0.03 (0.13)	0.05	2.14 (0.40)	1.99 (0.49)	-0.16 (0.17)	0.49	F[2,34]=2.07, η^2 =0.14
Percent Overweight	59.11 (28.96)	54.01 (30.88)	-5.10 (5.52)	0.48	59.42 (13.58)	59.47 (19.07)	0.04 (10.13)	0.00	69.92 (31.02)	61.43 (32.54)	-8.48 (7.83)	0.56	F[2,34]=3.29, η^2 =0.05
Waist Circumference (cm)	100.75 (18.73)	100.57 (21.44)	-0.18 (5.73)	0.00	100.60 (8.19)	99.04 (6.43)	-1.56 (5.30)	0.10	108.62 (14.16)	105.88 (13.71)	-2.75 (6.14)	0.18	F[2,31]=0.69, η^2 =0.51
DEXA % Fat	42.33 (7.78)	40.91 (9.74)	-1.42 (2.63)	0.24	45.77 (7.33)	45.48 (8.12)	-0.29 (1.89)	0.03	43.21 (5.07)	40.73 (5.09)	-2.47 (2.63)	0.48	F[2,34]=1.63, η^2 =0.21
DEXA Total Lean	41.41 (14.95)	42.19 (14.58)	0.78 (1.69)	0.19	35.71 (11.32)	37.27 (11.33)	1.56 (1.00)	0.74	47.33 (14.00)	47.93 (13.51)	0.59 (1.66)	0.12	F[2,34]=0.34, η^2 =0.71
Fasting Glucose (mg/dL)	90.87 (7.09)	89.80 (6.45)	-1.07 (6.86)	0.03	95.00 (10.32)	94.17 (4.83)	-0.83 (8.89)	0.01	87.41 (4.47)	87.76 (6.07)	0.35 (5.51)	0.00	F[2,34]=0.68, η^2 =0.51
Fasting Lipids (mg/dL)													
Triglycerides	105.60 (64.92)	120.80 (79.07)	15.20 (67.91)	0.05	99.17 (20.46)	132.17 (38.41)	33.00 (30.11)	0.59	108.53 (64.23)	105.06 (74.21)	-3.47 (50.76)	0.01	F[2,34]=0.98, η^2 =0.39
Total Cholesterol	160.27 (30.93)	158.33 (31.14)	-1.93 (22.01)	0.01	168.67 (9.69)	150.83 (20.63)	-17.83 (18.15)	0.54	160.53 (31.14)	155.06 (27.40)	-5.47 (20.12)	0.07	F[2,34]=1.05, η^2 =0.36
HDL Cholesterol	45.73 (7.60)	46.20 (10.52)	0.47 (6.48)	0.01	45.00 (6.75)	39.50 (4.42)	-5.50 (5.68)	0.53	49.41 (9.90)	49.65 (11.02)	0.24 (5.17)	0.00	F[2,34]=2.56, η^2 =0.09
LDL Cholesterol	93.93 (23.30)	87.93 (28.78)	-6.00 (19.16)	0.10	103.83 (11.13)	84.83 (17.70)	-19.00 (14.11)	0.69	89.41 (24.63)	85.06 (21.08)	-4.35 (13.26)	0.10	F[2,34]=1.34, η^2 =0.28
Secondary Behavioral Measures													
Aberrant Behavior Checklist													
Total Score	33.40 (24.60)	33.73 (28.84)	0.33 (15.65)	0.00	49.00 (17.94)	52.83 (22.50)	3.83 (12.16)	0.11	7.63 (15.12)	4.75 (6.55)	-2.88 (10.70)	0.07	F[2,33]=1.70, η^2 =0.20
Irritability Subscale Score	11.33 (9.04)	10.07 (8.55)	-1.27 (5.82)	0.05	15.83 (5.38)	18.83 (6.97)	3.00 (4.65)	0.33	2.31 (5.15)	0.94 (1.39)	-1.38 (4.32)	0.10	F[2,33]=6.89, η^2 =0.003
Child Behavior Checklist, Total Score	56.27 (28.91)	51.33 (29.06)	-4.93 (17.86)	0.08	70.50 (28.84)	68.83 (30.08)	-1.67 (22.16)	0.01	17.76 (15.66)	13.06 (10.04)	-4.71 (11.70)	0.15	F[2,34]=2.02, η^2 =0.15

*Main Effect of Time

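### In the last column of Table 2 every value labelled eta-squared is the p-value of the F beside it, and the column head misnames the test

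*Combined protocol and SAP*

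**What the plan says.** The table in question is "Table 2: Change in Additional Metabolic and Behavioral Measures by Treatment Group" in Appendix II. For each arm it prints the week-0 mean, the week-16 mean, the change and an eta-squared that the footnote defines as "Main Effect of Time". The last column, headed *Time x Treatment*, prints an F with its df and a second value that also carries the eta-squared symbol. Examples are "F[2,34]=1.16, η^2 =0.33" for Height, "F[2,34]=0.34, η^2 =0.71" for DEXA Total Lean and "F[2,33]=6.89, η^2 =0.003" for ABC Irritability. No number in the table is labelled as a p-value, and no arm sizes are printed.

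The Analytic approach paragraph in Appendix I describes the group comparison as an ANCOVA of the 16-week value in which "the predictors are the baseline value of the risk factor and the study group (three level factor". It states this for the three main risk factors and describes no repeated-measures model.

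**The concern.** An F and its df fix partial eta-squared exactly, so each cell can be checked against itself. An F below 1 on 2 and 34 df cannot go with an effect size of 0.71, and an F of 6.89 cannot go with one of 0.003. The column looks like p-values under the wrong symbol.

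If so, anyone who takes the column at its label, or lifts effect sizes from this pilot for a later power calculation or a meta-analysis, gets the order of the measures backwards. The three measures with p below 0.05, before any allowance for multiplicity, would appear to be the least affected.

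The head raises a second question. With two time points, the interaction F equals the one-way F on change scores, which is a different test from the ANCOVA in the Analytic approach.

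**Working it through.** **1. The label (inputs: only the F and df printed in Table 2).**

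Partial eta-squared = 2F / (2F + error df). The p-value is the upper tail of the F distribution on 2 and the printed error df.

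- Height: 2(1.16) / (2.32 + 34) = 0.064; p = 0.326; printed 0.33.
- Irritability: 2(6.89) / (13.78 + 33) = 0.295; p = 0.0032; printed 0.003.
- Total Lean: 2(0.34) / (0.68 + 34) = 0.020; p = 0.714; printed 0.71.

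| Measure | F (error df) | Printed as eta-squared | p from F | Partial eta-squared |
|---|---|---|---|---|
| Height | 1.16 (34) | 0.33 | 0.326 | 0.064 |
| Weight | 3.37 (34) | 0.05 | 0.046 | 0.165 |
| BMI z | 2.07 (34) | 0.14 | 0.142 | 0.109 |
| Percent Overweight | 3.29 (34) | 0.05 | 0.049 | 0.162 |
| Waist | 0.69 (31) | 0.51 | 0.509 | 0.043 |
| DEXA % Fat | 1.63 (34) | 0.21 | 0.211 | 0.087 |
| Total Lean | 0.34 (34) | 0.71 | 0.714 | 0.020 |
| Glucose | 0.68 (34) | 0.51 | 0.513 | 0.038 |
| Triglycerides | 0.98 (34) | 0.39 | 0.386 | 0.055 |
| Total Cholesterol | 1.05 (34) | 0.36 | 0.361 | 0.058 |
| HDL | 2.56 (34) | 0.09 | 0.092 | 0.131 |
| LDL | 1.34 (34) | 0.28 | 0.275 | 0.073 |
| ABC Total | 1.70 (33) | 0.20 | 0.198 | 0.093 |
| Irritability | 6.89 (33) | 0.003 | 0.0032 | 0.295 |
| CBCL | 2.02 (34) | 0.15 | 0.148 | 0.106 |

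All 15 printed values equal p at the printed precision; none equals partial eta-squared. Classical eta-squared cannot exceed partial eta-squared, and 11 of the 15 printed values do, so that definition does not rescue the label. The Spearman correlation between printed and correct values is -0.998.

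**2. The arm sizes (inferred, not printed).**

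For a one-arm change with mean m and standard deviation SD, eta-squared = n·m² / (n·m² + (n−1)·SD²). For usual-care Weight with n = 6: 6(2.42²) / (6(2.42²) + 5(2.36²)) = 35.14 / 62.99 = 0.56, as printed.

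Sizes of 15 (AP-BWI), 6 (AP-UC) and 17 (NP-BWI), with NP at 16 in the two ABC rows, reproduce all 39 within-arm values in 13 rows to within 0.01, and 34 of them exactly. Height is too coarsely rounded to use, and the arm split for Waist is unknown. So the within-arm columns do hold eta-squared. These sizes also give N−4 = 34 and 33, the printed error df for an ANCOVA with baseline and a three-level group.

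**3. The column head.**

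The ANCOVA can be rebuilt from the printed summaries. The within-arm covariance is (SD0² + SD16² − SDchange²)/2. Pool over arms to get the within sums Wxx, Wyy and Wxy, and add the between-arm terms to get the totals. Residual sums of squares are Wyy − Wxy²/Wxx with group in the model, and the same form on the totals without it.

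Glucose:
- With group: 1288.60 − 652.40²/1555.96 = 1015.05.
- Without group: 1472.04 − 873.10²/1831.33 = 1055.78.
- ANCOVA F = [(1055.78 − 1015.05)/2] / (1015.05/34) = 0.68. Printed: 0.68.
- Change-score F = (17.41/2) / (1539.76/35) = 0.20.

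| Measure | Printed F | Rebuilt ANCOVA F | Change-score F |
|---|---|---|---|
| Weight | 3.37 | 3.38 | 4.14 |
| Total Lean | 0.34 | 0.34 | 0.83 |
| Glucose | 0.68 | 0.68 | 0.20 |
| LDL | 1.34 | 1.34 | 1.95 |
| ABC Total | 1.70 | 1.70 | 0.62 |
| Irritability | 6.89 | 6.87 | 1.86 |
| CBCL | 2.02 | 2.01 | 0.10 |

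The ANCOVA F agrees within about 0.02 in 12 of 15 rows: these seven plus Percent Overweight, DEXA % Fat, Triglycerides, Total Cholesterol and HDL. The change-score F differs from print in 11 of those 12; HDL (2.56 against 2.58) does not separate the models, and neither does Waist. Height and BMI z cannot be settled: the rebuilt F is 0.61 and 1.73 from the printed week-16 means, or 1.07 and 2.03 from week 0 plus change, against 1.16 and 2.07 printed. A one-way test on 37 children would also have 34 error df, but the change-score values rule it out.

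**The case against.** The mislabel itself cannot be defended: it recurs in every row and follows from the printed numbers. The arguments on the other side concern its weight and the second charge.

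- *The head is loose, not wrong.* ANCOVA of the week-16 value and ANCOVA of the change, each adjusted for baseline, give the same group F, so the test does compare adjusted change between groups. That is true and makes the head the lesser point. But the head names the unadjusted interaction, and for several rows that test gives a very different F.
- *The usual-care size of 6 conflicts with Table 1, which prints n = 17 for that arm.* Table 1's own total gives 47 − 19 − 21 = 7. Its combined mean weight agrees: (19×77.08 + 7×72.37 + 21×85.76)/47 = 80.26, as printed. Six analysed at week 16 is consistent with seven at baseline.
- *The within-arm check is partly circular, since n was fitted to those cells.* This is fair. The printed error df and the rebuilt F values are the independent support.
- *ANCOVA is stated only for the three main risk factors.* This is also fair. Its use for the additional measures is inferred from the numbers.
- *F stands in the same cell, so a careful reader can recover the order, and the reversal adds no evidence beyond the mislabel.* Both are true. How readers use the column is a judgement, and no text in the documents interprets it.

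**Conclusion.** The concern holds. Fifteen of 15 values in the last column are p-values printed under the eta-squared symbol, and the table uses that symbol correctly in its other columns. This conclusion needs no assumption.

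The size varies by row. The error is gross for Irritability (0.003 against 0.295, about 98-fold too small), Total Lean (0.71 against 0.020, about 36-fold too large), Glucose and Waist, and modest for BMI z, HDL and CBCL. The three rows with p below 0.05 (Irritability 0.003, Weight 0.046, Percent Overweight 0.049) carry the three lowest printed values.

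That the head misnames the test also holds, on the inferred arm sizes of 15/6/17 (16 for NP in the ABC rows). The change-score F values show which test was run; they are not replacement results. This is a correction to a supplementary results table.

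**What to change.** In the last column of Table 2:

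- Relabel the second value as p, and print three decimals at least for Weight (0.046) and Percent Overweight (0.049), which both now appear as 0.05.
- Add partial eta-squared = 2F/(2F + error df) for each row, as tabulated above, so that the effect size the column set out to show is there. The relabelling alone removes the error.
- Rename the column to say that it is the group effect at week 16 adjusted for baseline (ANCOVA), and state that this model was used for the additional measures.
- Print the analysed n per arm, including the rows with 33 and 31 error df.

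Leave the ANCOVA and its F values as they are. The arm sizes can be read from the existing analysis output, so the cost is one table correction.
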